6.10.2. Clinical Laboratory Studies

At enrollment and every 8 weeks during follow-up for pregnant women venipuncture blood samples will be collected for routine clinical laboratory studies, including CBC and ALT measurements. In children venipuncture blood samples will be collected for a routine hemoglobin measurement using a portable spectrophotometer (HemoCue Angholm, Sweden) at 12, 28, and 52 weeks of age. Additional venipunctures will be performed, as appropriate, for laboratory testing to evaluate non-malarial medical illnesses at the discretion of study physicians. Results will be made available to study physicians in a timely manner for patient management decision-making. Additional hemoglobin measurements will be performed each time a patient is diagnosed with malaria using a portable spectrophotometer (HemoCue, Angholm, Sweden) and results will be immediately available.

6.10.3. Placental Studies

Cord blood will be collected for immunology studies described below. Placental blood collected for Giemsa-stained blood smears and future molecular studies will be obtained by making a small incision on the maternal surface of the placenta within 1 hour of delivery, collecting blood from the intervillous space via syringe, and then placing the blood in an EDTA tube. Placental tissue will be collected for histological assessment. Two 1 cm-wide full thickness biopsies from each placenta, obtained about 5 cm from the cord, will be obtained within 1 hour of delivery and placed in 10% neutral buffered formalin. Biopsy specimens will be embedded in paraffin wax, sectioned into 3 µM slices using a rotary microtome, fixed to glass slides, and dehydrated in sequential ethanol baths. Separate slides will then be stained in 0.1% hematoxylin and 1% eosin for 5 and 1 min, respectively, or in 2% Giemsa for 30 minutes. All necessary expertise and infrastructure for these studies is in place in Tororo. For assessment of histologic evidence of placental malaria, placentas will be graded into 5 categories using a standardized approach.⁷² The presence of intervillous parasite-infected erythrocytes and of pigment in monocyte/macrophages or fibrin will be noted. Quantitative assessments of placental malaria will be as follows. First, 1000 intervillous blood cells will be counted under high power. Percentages of intervillous erythrocytes infected with parasites and of monocyte/macrophages containing malarial pigment will be counted. Placental specimens will be examined by two experts, and any discrepant readings will be resolved by a third reader.

6.10.4. Molecular and Parasitology Studies

Each time a thick blood smear is obtained; blood will also be collected onto filter paper. Samples will be collected by venipuncture or by finger prick sampling. Blood will be placed onto filter paper in approximately 25 µl aliquots per blood spot (4 blood spots per sample). The samples will be labeled with study numbers and dates, air-dried, and stored in small, sealed sample bags at ambient temperature or 4°C with desiccant. Molecular studies will include the extraction of DNA from filter paper and followed by characterization of parasite genetics using standard molecular procedures including loop-mediated isothermal amplification (LAMP), DNA hybridization, and/or restriction enzyme digestion. Additional molecular studies will include analyses of polymorphisms in parasite genes and measurement of piperaquine drug levels from plasma samples. Molecular studies will be performed only for research purposes and will have no impact on the clinical management of study patients. Molecular studies will be formed in Uganda whenever possible and at UCSF when facilities/equipment are not available in Uganda. One exception will be for metabolic analyses of newborn bloodspots and cord blood for the purposes of gestational dating and examination of metabolite-outcomes relationships. Given the need to evaluate relationships using standardized mass spectrometry guidelines and referents, these tests will be done at the Iowa State Hygienic Laboratory in Ankeny, Iowa. Specimens will be collected using Gutherie card stock provided by the laboratory. Specifically, a 5 millimeter spot of 1) blood collected by heel stick or finger prick and 2) cord blood at birth (< 10 drops) will be deposited on card stock from the same lot that is provided by the Iowa lab. All specimens will be delivered to Iowa from Uganda by mail via freezer packs within one week of draw.

Blood collected by venipuncture or finger prick on the day malaria in child is diagnosed will be used in selected subjects for parasite culture, experimental MOD, standard RDT, microscopy, qPCR, parasite detection by magnetic levitation, and/or immunology studies (below). For these studies the skin will be prepped with 3 washes with a betadine or equivalent sterilizing solution, and then approximately 3-5 mls of blood will be collected in an anticoagulated sterile tubes and transferred promptly (generally within 30 minutes) to our molecular laboratory. Parasites will be cultured following standard protocols. In brief, erythrocytes will be separated from plasma by centrifugation and removal of the supernatant and buffy coat, and the infected erythrocytes will then be cultured in RPMI medium supplemented with human serum or Albumax serum substitute. Cultured parasites will be evaluated for in vitro drug sensitivity, molecular characteristics, and other features to characterize antimalarial drug resistance and other aspects of malaria. Information from the parasitology studies will have no impact on patient care.

CareStart Pf HRP-2 (Access Bio Inc USA) RDT testing using the PTS reader will be performed at enrollment and every 4 weeks at the time of routine visits during pregnancy. Approximately 5 μ L of whole blood will be placed on the cartridge, which is inserted into the reader, and the reader will take approximately 1-3 minutes to complete the testing. The graphical user interface (GUI) guides the user through the assay process. Quantitative PCR will be performed at enrollment and at the time of routine visits using standardized procedures on \sim 100ul of whole blood. A HRP2-based experimental RDT will be tested at enrollment and every 8 weeks at the time of routine phlebotomy during pregnancy using \sim 100ul of whole blood. An RDT result will be considered positive if both the control line and the test line are visible after the development time. A result will be considered negative if the control line is visible, but no test line appears. The result will be considered invalid if no control line is visible, regardless of whether or not a test line appears. A hemozoin-based experimental rapid diagnostic test (MOD) will be performed at routine visits in a subset of children using ~ 50ul of whole blood collected by finger prick or phlebotomy. Approximately 50ul of whole blood will be placed in a special cuvette with a custom dilute, which is inserted into the sonicator and then the reader, and it will take approximately 2 minutes to complete the testing. For samples undergoing parasite detection by magnetic levitation, less than 10 µL of blood will be mixed with a paramagnetic

agent such as gadolinium, placed in close proximity to the earth magnets, and visualized by microscopy and/or a magnified imaging system.

Procedures for reporting and follow up of incidental concerning metabolite testing results Participants will be considered at elevated risk for Sickle Cell Disease (SCD) or Congenital Hypothyroidism (CH) according to the following criteria:

 SCD: Patterns of adult hemoglobins [HbA(A) and variants (S,C,D,E, B-thal)] as well as hemoglobin peak percentages (HGB-FAST, HGB-F1, HGB-F, HGB-F+F1, HGBFAST+ F1, HGB-Other, HGB-A] based on the interpretation of the lowa testing laboratory.

• CH: thyroid stimulating hormone> levels >50 mIU/L from cord blood sample The metabolite laboratory will send results and IDs for all participants with concerning results. The Ugandan team will ask the participant and parents to come to clinic when the will explain that the metabolite testing results suggest the possibility of a disease, but do not constitute a true diagnosis. The team will explain offer to perform confirmatory testing using standard clinical tests; if the participant is found to have the disease of concern, the study team will offer treatment free of charge. A blood specimen would then be obtained for confirmatory testing by a local commercial lab, including Hemoglobin Electrophoresis for concern of SCD and TSH and T4 testing for concern for hypothyroidism. Patients will receive care for these conditions by the study team during study follow up and be referred to local providers for care at the conclusion of the study

6.10.5. Immunology Studies

Venipuncture blood samples collected at enrollment, during routine visits done every 8 weeks in pregnant women and at 12, 28, and 52 weeks of age in children, and in select subjects on the day malaria is diagnosed (above) will be made available for immunology studies. Approximately 15mls of blood in pregnant women and 5mls of blood in children will be collected and separated into plasma and peripheral blood mononuclear cells (PBMC) using a Ficoll gradient, following standard protocols. Plasma will be stored at -80°C for future immunology studies, which may include measurement of levels of cytokines, antibodies, and other features related to the host immune response. PBMCs will be stored in liquid nitrogen to maintain viability, and will be evaluated using flow cytometry, ELISPOT, RT-PCR, gene expression microarrays and other assays to assess the host immune response. Stool will be collected in in select children at 4 and 52 weeks of age and stored for future studies analyzing the influence of parasitic and bacterial infections on immunity. Information from immunology studies will have no impact on patient care. Immunology studies will be done in Uganda whenever possible. However, due to technological limitations some immunology studies may be done at UCSF.

6.10.6. Sample Storage for Future Use

Certain biologic specimens (placenta, filter paper, plasma, stool, and PBMC) will be stored in our laboratories for future molecular and immunology studies, pending participant consent for future use of biological specimens obtained during the course of the study. Samples will generally be stored in our laboratory in Tororo, Uganda. Certain specimens requiring long term freezer storage (plasma, PBMC) may be transferred for long-term storage to our laboratory in Kampala, Uganda (IDRC Molecular laboratory) or a specialized specimen bank with our collaborators at UCSF (Department of Medicine, [name]). With consent for future use, sample retention will generally be open ended. Samples that do not have consent for future use, as detailed above, will be destroyed upon completion of clinical studies. Samples will be destroyed following SOPs which comply with local regulations and guidance.

6.11. Co-enrollment Guidelines

The pregnant women and children from this study may be co-enrolled in observational studies. They may not be co-enrolled in protocols that utilize concomitant study medications. Coenrollment in other studies will be determined on a case-by-case basis by the protocol team.

6.12. Management of Adverse Events Potentially Related to Study Drugs

The following section outlines management of adverse events potentially related to study drugs (SP or DP) among pregnant women. Given the double blinded nature of the intervention, study clinicians and study participants will not be aware of what study drugs are being administered. Therefore all women will be considered potentially exposed to either study drug during the period study drugs are first given up to the completion of follow-up (6 weeks post-partum).

6.13. Grade 1 or 2 Adverse Events

Participants who develop grade 1 or 2 adverse events may continue study drugs. The study clinicians will manage the grade 1 or 2 events according to standard practice.

6.14. Grade 3 or 4 Adverse Events

Management will be as follows:

 Repeat observation or lab test within 72 hours of observation or of receiving lab results report.

- Work-up to exclude other causes.
- For grade 3 or non-life threatening grade 4 adverse events, subjects may continue taking study drugs pending clinic visit or repeat laboratory tests. Clinician has the option of immediately stopping the study drugs if subject cannot be examined in clinic, if a repeat laboratory test cannot be performed within 72 hours, or if the clinician determines that the continuation of study drugs is unsafe while awaiting clinic exam or test results.
- For grade 4 life-threatening adverse events, study clinicians should hold study drugs pending laboratory confirmation.
- For all grade 3 or 4 adverse events supported by repeat clinical exam or laboratory test
 results, study drugs will be held, and laboratory tests will be repeated every 1-2 weeks, until
 the adverse event resolves to < grade 2 unless there is strong evidence that the adverse
 event is not related to either study drug.
- If the adverse event persists at grade 3 or 4 for more than 28 days or recurs on re-challenge, and the adverse event is thought to be possibly related to one of the study drugs, the study drugs will be permanently discontinued.

In the event that study drugs are permanently discontinued, study participants will remain in the study, following our intention-to-treat analysis approach. In the event that study drugs are permanently discontinued, study clinicians may become un-blinded to the study participant assigned treatment regimen if this knowledge may assist in the management of the grade 3 or 4 adverse event(s) that lead to the permanent discontinuation of the study drugs.

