4.2. Exclusion Criteria

- 1) History of serious adverse event to SP or DP
- 2) Active medical problem requiring inpatient evaluation at the time of screening
- 3) Intention of moving outside of Busia District, Uganda
- 4) Chronic medical condition requiring frequent medical attention
- 5) Prior SP preventive therapy or any other antimalarial therapy during this pregnancy
- 6) Early or active labor (documented by cervical change with uterine contractions)

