7.1.3. Reporting of Adverse Events

Guidelines for reporting of adverse events provided by NICHD, UCSF Committee for Human Research (CHR), and the Food and Drug Administration (FDA) in the U.S. and the Makerere

University IRB (SBSREC), and National Drug Authority (NDA) in Uganda will be followed as summarized in Table 2 below.

Institution	Type of Adverse Events	When to Report
UCSF-CHR	 External (off-site) Adverse Events are: AEs that occur in study participants who are not enrolled at a UCSF or affiliated study site. These AEs occur at sites that are under the oversight of another IRB. 	• Not applicable
MU-SBSREC	All Serious and Unexpected events irrespective of relationship	 Fatal or life-threatening events within 3 working days of awareness All other SAEs within 7 calendar days
NDA	All Serious and Unexpected events irrespective of relationship	• Within 7 calendar days of awareness
FDA	 Definitely, Probably or Possibly related AND BOTH Serious[*] AND Unexpected[±] 	 For fatal or life-threatening events, by telephone or fax within 7 calendar days of first awareness All other reportable events within 15 calendar days of first awareness

Table 2. Guidelines for reporting adverse events

Serious Adverse Event (SAE) is any AE that results in any of the following outcomes:

- Death,
- Life-threatening adverse experience.
- Inpatient hospitalization or prolongation of existing hospitalization,
- Persistent or significant disability/incapacity,
- Congenital anomaly/birth defect, or cancer, or

• Any other experience that suggests a significant hazard, contraindication, side effect or precaution that may require medical or surgical intervention to prevent one of the outcomes listed above,

• Event that changes the risk/benefit ratio of the study.

Unexpected Adverse Event An adverse event is defined as being unexpected if the event exceeds the nature, severity, or frequency described in the protocol, consent form and investigator brochure (when applicable). An unexpected AE also includes any AE that meets any of the following criteria:

- Results in subject withdrawal from study participation,
- Due to an overdose of study medication, or
- Due to a deviation from the study protocol

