8.1.3. Analyses

A modified intention-to-treat approach to all analyses will be used, including all study participants randomized to therapy and have the outcome of interest measured including all

follow-up time until the study participants complete the study or early study termination regardless of whether the intervention was stopped due to an adverse event.

Primary analysis. We will compare the risk of having any adverse birth outcome between the study arms using the Chi-Square or Fisher's exact test. We will explore for any differences of potential confounders between the treatment arms and if necessary adjust our analysis using multivariate logistic regression. We will also perform sub-group analyses comparing the risks of having individual adverse birth outcome (LBW, preterm delivery, SGA) between the study arms using the Chi-Square or Fisher's exact test.

Secondary analyses. We will compare the prevalence of different definitions of placental malaria (placental parasitemia by microscopy, placental malaria by LAMP, placental malaria by histopathology) using the Chi-Square or Fisher's exact test. We will compare the incidence of maternal malaria and adverse events using Poisson or negative binomial regression models. The Poisson models will include the logarithm of the follow-up time as an offset. We will translate the fitted coefficients and their confidence bounds into percentage effects with the formula 100*[exp(coefficient)-1]. This approach is closely related to exponential survival models for analyzing events per follow-up time, but is better able to adjust for violated assumptions. Testing for overdispersion in the Poisson regression can detect violations of these assumptions, and variances can be adjusted accordingly to produce valid p-values and confidence interval. If significant deviations from required distributions in study data are detected, we will employ negative-binomial or zero-inflated negative-binomial models to account for the observed pattern of data. We will compare the prevalence of maternal anemia and asymptomatic parasitemia using generalized estimating equations with adjustments for repeated measures in the same study participant. If necessary, multivariate analyses will be performed to adjust for potential confounders and effect modifiers.

8.2. Hypothesis 2

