- Any problems with study conduct, enrollment, sample size and/or data collection.

The first meeting of the DSMB will take place prior to the initiation of the study to discuss the protocol and the Data Safety Monitoring Plan. Meetings of the DSMB shall be held according to the plan outlined above. Meetings shall be closed to the public because discussions may address confidential patient data. Meetings may be convened as conference calls as well as in person. An emergency meeting of the Board may be called at any time should questions of patient safety arise. The DSMB may request the presence of study investigators at such meetings.

The study PI will distribute study information to the DSMB at least 10 days prior to a scheduled meeting. The DSMB may request additions and other modifications to this information on a one-time or continuing basis. This information will consist of two parts: (1) information on study progress such as accrual, baseline characteristics, and other general information on study status and (2) any confidential data on study outcomes, including safety data. A formal report from the DSMB should be supplied to the PI within 6 weeks of each meeting. Each report should conclude with a recommendation to continue or to terminate the study. This recommendation should be made by formal majority vote. A recommendation to terminate the study should be transmitted to the PI, IRBs and NIH as rapidly as possible, by immediate telephone and fax if sufficiently urgent. In the event of a split vote in favor of continuation, a minority report should be contained within the regular DSMB report.

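### Section 6.14 does not require the study drug to be stopped after a first, possibly related life-threatening event that resolves within 28 days

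*Combined protocol and SAP*

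**What the plan says.** Section 6.14 sets out how grade 3 and 4 adverse events are handled. On first recognition of the most serious ones, the instruction is: "For grade 4 life-threatening adverse events, study clinicians should hold study drugs pending laboratory confirmation". Once any grade 3 or 4 event is confirmed, drugs are held and tests repeated until "the adverse event resolves to < grade 2 unless there is strong evidence" that neither study drug caused it. Permanent discontinuation becomes compulsory under one condition, "If the adverse event persists at grade 3 or 4 for more than 28 days or recurs on re-challenge", and only if the event is thought possibly related.

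Follow-up after a stop is already settled. Section 6.14 states: "In the event that study drugs are permanently discontinued, study participants will remain in the study, following our intention-to-treat analysis approach". Section 8.1.3 likewise keeps follow-up time "regardless of whether the intervention was stopped due to an adverse event".

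At entry, the first exclusion criterion in section 4.2 is "History of serious adverse event to SP or DP".

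**The concern.** Hold, wait for resolution and re-challenge is a reasonable scheme for laboratory toxicities. It suits poorly those clinical events in which re-exposure can itself be life-threatening. Appendix I grades acute anaphylaxis, Stevens-Johnson syndrome and torsade de pointes as 4, and section 6.14 handles them under the same rule as a low hemoglobin. By making recurrence on re-challenge one of the two tests for stopping, the rule contemplates giving the same blinded drug again.

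A woman with a known serious reaction to SP or DP would be kept out at screening, while one who has such a reaction during the trial is not, by rule, taken off drug. That is a contrast rather than a contradiction, since the exclusion criterion governs entry only. What is at stake is the safety of an individual woman in a very rare case.

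**Working it through.** The plan gives no figure on this point to reproduce. The check applies the rule to the scenario, looks for a compulsory stop elsewhere, and then sizes the problem.

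**1. Applying section 6.14.** Take a first event that is possibly related, grade 4, clinically life-threatening, and below grade 2 before 28 days have passed.

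- Immediate action: hold.
- After confirmation: hold, with repeat testing until below grade 2.
- Duration limb (more than 28 days at grade 3 or 4): not met.
- Recurrence limb: cannot be met until she has been dosed again.
- Result: no compulsory stop. The only required action is a hold.

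**2. Other places where a compulsory stop could sit.**

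- Section 6.14, clinician's option to stop at once: written for grade 3 and non-life-threatening grade 4 events awaiting examination or results.
- Section 6.9: the site investigator may withdraw a woman in her best interest. This is discretionary, and it concerns leaving the study rather than stopping the drug.
- Section 7.1.3: serious and unexpected events go to the local ethics committee ("Fatal or life-threatening events within 3 working days of awareness"). This is reporting only.
- Section 8.5.1: "An emergency meeting of the Board may be called at any time should questions of patient safety arise". This does not require one woman's drug to be stopped.
- Section 8.5.3: deals with stopping the whole study.

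**3. What re-dosing would look like.** Courses are 4 weeks apart (section 5.3), so an event that resolves within a cycle can meet the next scheduled course. The second and third daily doses of DP or its placebo are taken at home (section 5.4). Section 6.14 offers unblinding only after permanent discontinuation. ECGs are scheduled at 20, 28 and 36 weeks (section 6.5), so a re-challenge at 24, 32 or 40 weeks has none scheduled. By Appendix D, the courses left after a reaction at week g are (40 − g)/4, from 6 at week 16 to 0 at week 40.

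**4. Expected number of events on SP.** Inputs are 391 women per arm (section 5.1) and the UK long-term prophylaxis rates in the SP risk text of section 10.6.2: serious reactions 1:2,100, serious dermatological reactions 1:4,900, deaths 1:11,100. The assumptions are that these rates apply per woman and that the deaths are among the serious reactions. The chance of at least one event is 1 − exp(−expected number).

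| Event | Expected number | Chance of at least one |
|---|---|---|
| Serious | 391/2,100 = 0.19 | 17% |
| Serious dermatological | 391/4,900 = 0.08 | 8% |
| Serious, non-fatal | 391 × (1/2,100 − 1/11,100) = 0.15 | 14% |

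Only the non-fatal reactions could be followed by re-dosing. The same text says severe toxicity is much less frequent with African treatment regimens. Taking 2 to 10 times lower as an assumed range gives 0.151/2 = 0.075 down to 0.151/10 = 0.015. The documents give no rate of anaphylaxis or torsade for DP.

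**5. Extra stops under a stricter rule.** The earlier trial randomized 106 + 94 + 100 = 300 women (section 1.2). Its one possibly related grade 3-4 event was an anemia (section 10.6 text and Table 9), so there were 0 of any other kind in 300. The one-sided 95% upper bound is 1 − 0.05^(1/300) = 0.0099, or 1.0%. Applied to this trial, 782 × 0.0099 = 7.8, about 8 women, assuming the same rate here.

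**The case against.** The strongest reply is that this is a drafting preference of negligible consequence. No sentence orders re-dosing. The word governing resolution in 6.14 may limit only the repeat tests, so the text need not mean that dosing resumes. The section relies on clinical judgement throughout, and section 6.9 adds a discretionary exit. Few physicians would re-dose after anaphylaxis.

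The reply also challenges the figures. The 1:2,100 rate covers all serious reactions, not just life-threatening ones, and comes from long-term prophylaxis in a different population. Harm further requires resolution in time for another course and a physician who chooses to give it. The bound of about 8 women covers a wider class of events than the proposed rule, and 200 of the 300 earlier women (106 + 94) were on 3-dose rather than monthly regimens. A compulsory stop at possible relatedness also costs preventive courses when causality is doubtful.

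Much of this stands. The risk is very small, the sizing is rough, and clinicians can avoid re-dosing under the present text. It does not remove the gap. On either reading of the resolution clause, no stop is required after a first event, and the stated rule covers these events and uses re-challenge as a test for stopping. Discretion to do the safe thing is weaker than a written requirement for the worst case.

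**Conclusion.** The concern holds as a minor point. The reading rests on the text of 6.14 and the absence of any other compulsory rule, and confidence in it is high. The size is very small: about 0.15 non-fatal serious SP reactions across the trial if the UK rates apply per woman and include the deaths, and 0.015 to 0.075 if African risk is 2 to 10 times lower. These figures overstate the specific risk, because not every serious reaction is life-threatening and not every clinician would re-dose. The DP side cannot be sized from the documents.

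**What to change.** Add one sentence to section 6.14. A confirmed clinical life-threatening event, or a serious hypersensitivity, severe cutaneous or ventricular arrhythmic event, that is at least possibly related to study drug leads to permanent discontinuation without re-challenge, with follow-up continued under intention-to-treat. The same sentence should say that grade 3 or 4 laboratory abnormalities without life-threatening clinical consequences, such as hemoglobin below 6.5 g/dL (grade 4 for women in Appendix I), stay under the existing hold and re-challenge rule. The earlier trial's anemia, seen after the first and second doses, would stay there too, assuming it was not clinically life-threatening. Grade 3 QTc prolongation without arrhythmia would also remain under the existing rule unless the sponsor chooses to name it.

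The cost is small: no change to sample size, visits or analysis. The downside is a few more discontinuations, with an upper bound of about 8 of 782 women on the assumption above. A woman whose event was in fact unrelated would lose her remaining preventive courses, at most 6.
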